Several studies have assessed the prevalence of overactive bladder among different population age groups, ethnicities, or genders with varying results. It was rated to be 11.8% in a multicenter cross-sectional study including several countries in Canada and Europe (Germany, Italy, Sweden, and the UK (Irwin et al., 2006), while in the USA it was estimated to be 16% (Stewart et al., 2003). All these studies were conducted on the general population; however, in China, it was about 6% among university students (Liang et al., 2022).

In the Arab world, several cross-sectional studies have also assessed the prevalence of overactive bladder, including students, and its effect on the quality of life. Hajjar 2022 (Hajjar et al., 2022) assessed its prevalence among Lebanese female nulliparae university students. They showed that nocturia and frequency were the most common symptoms that bothered students. They also found a statistical correlation between smoking, drinking coffee, or tea, and increased symptoms. Also, drinking soft drinks was associated with an increase in urinary leakage. Additionally, Abuorouq 2024(Abuorouq et al., 2024) and Shawahna 2021(Shawahna et al., 2021)

Cross-sectional studies were conducted on medical students in Jordan and Palestine, respectively. They reported a prevalence of 44.5% and 54.1%, respectively. Shawahna 2021(Shawahna et al., 2021) reported a statistically significant correlation between gender or stressful life and a decrease in quality of life.

Rational

In Egypt, the prevalence of overactive bladder is underestimated. A single previous multinational cross-sectional study across several Arab countries, including Egypt, was conducted. (Al Edwan et al., 2021) was conducted in Egypt, Algeria, Jordan, and Lebanon among women. They reported a prevalence of 57.5% among Egyptian women.

Since this study, no study has been conducted to further assess its prevalence in different age or gender groups in Egypt. Taking into consideration the stressful life of medical students in Egypt, and several life risk factors they face, we will conduct this cross-sectional study.

No previous cross-sectional study was conducted on the medical students in Egypt before.

We aim to assess the prevalence of overactive bladder among Egyptian medical students. We will also assess the risk factors associated with an increase in this condition and its effect on their quality of life.

Research Questions

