What is the prevalence of the overactive bladder among Egyptian medical students, how can this affect their quality of life, and what are the risk factors that can increase its prevalence?

Hypothesis

We hypothesize that overactive bladder is a common condition in Egyptian medical students.

Aim:

Improve the quality of life of medical students by addressing the prevalence of overactive bladder and its risk factors

Objective

- To assess the prevalence of overactive bladder among Egyptian medical students.
- To assess its effect on their quality of life
- To address the risk factors that can increase the prevalence of this condition.

Methodology

A. Technical design

- **Study design:** Analytical cross-sectional study
- **Study sitting:** a medical student in Egypt will be accessed through an online questionnaire.
- **Study population:** Egyptian Medical students studying medicine in Egypt.
- **Time:** 2025-2026
- **Inclusion criteria**
 - Medical student studying human medicine in Egypt
 - Their age ranges from 18 to 27 years old
 - Egyptian person
- **Exclusion criteria**
 - Incomplete data
 - Wrong data in the questionnaire
 - Students refuse to participate

- **Sampling**

We calculated the sample size based on the total medical students in Egypt, which is 121,320, according to the Central Agency for Public Mobilization and Statistics (CAPMAS) 2023-2024(*Capmas*, n.d.). The expected prevalence of overactive bladder is 50%(Abuorouq et al., 2024; Shawahna et al., 2021). Using the total sample size, expected prevalence rate, an 80% power, 95% confidence interval (95% CI), and a 5% error margin, we calculated the sample size via Epi Info version 7.2.60(*Epi InfoTM | CDC*, n.d.) to become 384, and adding a 10% non-response rate, the final sample size will be 422 students

- **Sampling techniques:** The convenient sampling will be applied in this study

B. Operational design

- **Pilot study:** We will perform a pilot study to assess the readability of the questionnaire. We will perform it on 40 students, and any changes in the questionnaire will be made. Pilot study data will be excluded from the data analysis
- **Study field:** an online questionnaire will be shared through social media platforms such as WhatsApp, Facebook, or Telegram.

Data collection method

Students are required to fill out the online questionnaire. It is divided into three main categories.

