1. Sociodemographic data in which we ask about students' age, sex, and academic year. We also ask about their life risk factors, such as body weight, presence of chronic disease, previous surgery, stressful life, and soft drinks(Abuorouq et al., 2024).
2. Questions about the presence of overactive bladder symptoms.(Coyne et al., 2015) The questions are taken from the 6-item ask about the presence of overactive bladder symptoms in the past 4 weeks

This scale consists of 6 items, and each one has 6 available answers that range from not at all, which indicates the absence of the symptoms, to a very great deal, which indicates the presence of these symptoms. The score of each question ranges from 1 to 6, and the total score is 36. A score of 18 or more indicates the presence of the overactive bladder symptoms

3. Part 3 asks about the quality of life affected by the overactive bladder. This part is taken from the quality of life questionnaire part of the Overactive Bladder Symptom and Health-Related Quality of Life Short-Form (OAB-q SF)(Coyne et al., 2015). This is a 13-item questionnaire, each one has 6 answers (None of the time, a little of the time, some of the time, A good bite of the time, Most of the time, All of the time). Each question scores from 1 to 6, so the total score ranges from 13 to 78

- **Statistical analysis**

We will summarize the data first according to its type. Categorical data will be summarized into numbers and percentages, while continuous data will be assessed for normality first; if it is normally distributed, we will use mean and standard deviation (SD), and if not, median and interquartile range will be used (IQR).

Differential statistics will be conducted via the Mann-Whitney U test. We will assess the difference between the baseline data, such as sex, academic year, on the overactive bladder prevalence and its effect on quality of life.

Also, we intended to perform a logistic regression to assess the relation between overactive bladder symptoms and quality of life, and the relation between risk factors, such as history of UTI, soft drinks, coffee, or tea, on the presence of overactive bladder symptoms.

All statistics will be conducted using SPSS version 29.

C. Administrative design

- **Ethical considerations**

- The study protocol will be approved by the Institutional Review Board of Zagazig University, Faculty of Medicine
- Study participants will be included after informed consent.

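### The objective concerns factors that raise prevalence, but at the expected 50% prevalence the planned logistic odds ratios do not approximate prevalence ratios, and no adjusted prevalence-scale estimate is planned

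*Protocol*

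**What the plan says.** The Research Questions section of the protocol asks "what are the risk factors that can increase its prevalence", and the third item under Objective repeats it: "To address the risk factors that can increase the prevalence of this condition".

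Under Technical design the study is an "Analytical cross-sectional study". The Sampling paragraph states "The expected prevalence of overactive bladder is 50" per cent and cites two surveys of students. The background gives the results of those surveys, in Jordan and Palestine: "They reported a prevalence of 44.5% and 54.1%, respectively". It also gives a much lower figure: "in China, it was about 6% among university students".

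The outcome is made binary under Data collection method: "A score of 18 or more indicates the presence of the overactive bladder symptoms".

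Under Statistical analysis, logistic regression is the only model named for "the relation between risk factors, such as history of UTI, soft drinks, coffee, or tea, on the presence of overactive bladder symptoms". The same section plans numbers and percentages for categorical data, and a comparison of overactive bladder prevalence by baseline characteristics such as sex and academic year. The protocol names no effect measure for the regression and does not say how its coefficients will be worded. No statistical analysis plan was available for this review.

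**The concern.** A logistic model reports odds ratios. These lie close to prevalence ratios only when the outcome is uncommon, and this protocol expects it in about half of the students. A cross-sectional design can estimate prevalences directly, so nothing in the sampling forces the odds ratio as the only measure.

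What is at stake is the reading of effect size. The question is put in terms of prevalence, so a reader may take an adjusted odds ratio of 2 for coffee or soft drinks as a doubling of prevalence. At the planned prevalence the actual increase would be well short of that, and the importance of the factor would be overstated. Whether an association is found, and in which direction, is not at stake.

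**Working it through.** **Inputs from the protocol.** Expected prevalence 50% (Sampling); source surveys 44.5% and 54.1%, and the low contrasts of 6% and 16% (background); analysable sample 384 (Sampling).

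**Assumptions.** The protocol gives neither the share of students exposed to each factor nor an expected effect. Exposed shares f of 20%, 50% and 80% and a range of effects are therefore assumed. All figures are crude (unadjusted).

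**The plan's own figure.** 1.96² × 0.5 × 0.5 / 0.05² = 384, and 384 × 1.10 = 422. Both stated numbers are reproduced. This calculation is for the precision of one prevalence and does not involve the regression.

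**Relation between the two measures.** Let p0 be the prevalence in unexposed and p1 in exposed students.

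- PR = p1/p0, so PR − 1 = (p1 − p0)/p0.
- OR = [p1/(1 − p1)]/[p0/(1 − p0)], so OR − 1 = (p1 − p0)/[p0(1 − p1)].
- Dividing, (OR − 1)/(PR − 1) = 1/(1 − p1).

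If overall prevalence is 50%, any factor that raises prevalence has p1 above 0.5. The excess of the odds ratio over 1 is then more than twice that of the prevalence ratio, whatever the exposed share.

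**Examples at 50% overall, half exposed.** Here p0 = 1 − p1, so OR = PR².

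| Unexposed | Exposed | PR | OR | (OR − 1)/(PR − 1) |
|---|---|---|---|---|
| 47.6% | 52.4% | 1.10 | 1.21 | 2.10 |
| 45% | 55% | 1.22 | 1.49 | 2.22 |
| 40% | 60% | 1.50 | 2.25 | 2.50 |

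In reverse, an odds ratio of 2 is a prevalence ratio of 1.36, 1.41 or 1.47 for exposed shares of 20%, 50% or 80%.

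**Effects the study can detect.** With 384 students, 80% power and a two-sided 5% test, the smallest detectable crude contrast is:

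- half exposed: 42.9% against 57.1%, PR 1.33 and OR 1.78;
- 20% exposed: 46.5% against 64.2%, PR 1.38 and OR 2.06.

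The gap is therefore present at the effects this sample can find, with the excess inflated about 2.3 to 2.8 times.

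**Dependence on prevalence.** For PR 1.50 with half exposed, p0 = (overall prevalence)/1.25 and p1 = 1.5 × p0:

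| Overall prevalence | p0 | p1 | OR |
|---|---|---|---|
| 6% | 4.8% | 7.2% | 1.54 |
| 16% | 12.8% | 19.2% | 1.62 |
| 44.5% | 35.6% | 53.4% | 2.07 |
| 50% | 40.0% | 60.0% | 2.25 |
| 54.1% | 43.3% | 64.9% | 2.43 |

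The gap is negligible at 6%, small at 16%, and substantial at the prevalences on which the protocol bases its plan.

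**The case against.** The strongest reply is that logistic regression is a valid choice and the question asks which factors matter. For a binary exposure the crude odds ratio exceeds 1 exactly when the prevalence ratio does, the test of no association is sound, and the protocol nowhere promises a ratio of prevalences. All of this stands. A reader might infer that the model is wrong or should be replaced; the protocol does not support that.

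A reader might also infer that prevalence is never compared between groups. That is not so: percentages and a comparison by sex and academic year are planned. What is absent is an adjusted prevalence-scale estimate for the risk factors.

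A third inference would be that the odds ratios must greatly overstate every factor. The 50% is a planning value, and even there a weak factor shows 1.10 against 1.21.

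The design gives a further reason not to replace the odds ratio. Recruitment is a convenience sample through social media. Suppose, as an illustration, that the true prevalences are 30% and 20% and that cases are three times as likely to respond. The sample then shows 0.9/(0.9 + 0.7) = 56.3% and 0.6/(0.6 + 0.8) = 42.9%. The prevalence ratio falls from 1.50 to 1.31, while the odds ratio stays at 1.71. Selection on the outcome alone distorts the prevalence ratio and leaves the odds ratio unchanged. The added estimates must therefore stand beside the odds ratios.

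Finally, the effect measure could be left to a statistical analysis plan. Its absence from the protocol is not the point. Three things the protocol does state (a prevalence question, an expected 50% and a logistic model) leave the question answered on a scale other than the one on which it is asked.

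**Conclusion.** The point holds as a modest improvement. At the expected prevalence the odds ratio is not a usable stand-in for the prevalence ratio. Its excess over 1 is more than doubled for any factor that raises prevalence at 50% overall, and an odds ratio of 2 means a prevalence increase of roughly 36% to 47%.

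This rests on an observed prevalence near the planned 50%, on assumed exposed shares of 20% to 80%, and on crude figures. Adjusted values will differ. The harm also depends on the odds ratios being read as prevalence ratios, which the wording of the objective invites but the protocol does not itself do. Nothing here invalidates the planned tests or changes the sample size.

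**What to change.** - Keep the logistic regression and report its odds ratios as planned.
- For each risk factor add an adjusted prevalence difference and prevalence ratio with confidence intervals from the same covariates, by marginal standardisation of the logistic model or by Poisson regression with robust standard errors.
- State that odds ratios will not be worded as ratios of prevalence.
- State as a limitation that the added estimates depend on the prevalence in a self-selected convenience sample and can be distorted if symptomatic students respond more readily.

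The cost is one extra column per regression table and a sentence or two of text. The generalized linear models procedure in SPSS, the package already chosen, can fit the robust Poisson model. No extra data, questionnaire items or participants are needed.
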